8.6.1.3.2 Thrombotic Thrombocytopenic Purpura (TTP)

TTP has been reported following use of clopidogrel. It is characterized by thrombocytopenia, microangiopathic hemolytic anemia, neurological findings, renal dysfunction, and fever.

8.6.1.3.3 Non-Hemorrhagic Adverse Reactions

In the TRA 2°P / TRA•CER study, non-hemorrhagic adverse reactions specified below occurred at least 2% in the vorapaxar group and at least 10% greater than placebo.

- Anemia
- Depression
- Rashes, eruptions, and exanthemas

8.6.1.3.4 Iron Deficiency and Oculomotor Disturbances

The following adverse reactions below occurred at a rate less than 2% in the vorapaxar group but at least 40% greater than placebo in descending order:

- Iron deficiency
- Retinopathy or retinal disorder
- Diplopia/oculomotor disturbances

An increased rate of diplopia and related oculomotor disturbances was observed with vorapaxar treatment (30 subjects, 0.02% vs. placebo (10 subjects, 0.06%). While some cases resolved during continued treatment, information on resolution of symptoms was not available for some cases.

8.6.1.3.5 Allergic Reactions

Subjects may experience an allergic response to vorapaxar/clopidogrel or any its component. Discontinue study treatment if signs and symptoms of an allergic reaction are noted.

8.6.1.3.6 Pain, discomfort, or bruising

Pain, discomfort, or bruising from phlebotomy sites may occur related to the blood sampling process. Fainting and a decrease in blood pressure can happen although rare.

There is also a very small risk that a nerve could be damaged during insertion of a needle. Phlebotomy sites will be carefully chosen to minimize risk.

8.6.1.3.7 Mild discomfort in the arm from a pressure cuff

Subjects may experience mild discomfort in the arm from a pressure cuff while inflated as related to blood pressure measurement and Endo-PAT2000 test.

8.6.1.3.8 Local irritation

Local irritation from ECG electrodes may occur. Some hair may need to be clipped in small patches to accurately measure an ECG. Removal of electrodes may cause local irritation and rash.

8.6.1.3.9 Other potential adverse events

Other potential adverse events as related to subject's concomitant diseases. To prevent subjects from missing any medications while in-clinic, all subjects will be instructed to take all approved concomitant medications (i.e., insulin, anti-hypertensive medications) with them to be taken as allowed by study protocol. A small snack will also be provided to subjects after laboratory and endo-pat testing to prevent hypoglycemic episodes, especially for diabetic patients. Water will be allowed throughout each outpatient visits.

8.6.2 Economic risk

Subjects in the study may lose time at work or home and spend more time in the research site more than usual. Visit schedules will be made flexible for subjects (as allowed by protocol).

8.7 Benefits and Alternatives

There are no direct benefits to the patient. This study can help healthcare providers in understanding the mechanism of action of vorapaxar when added to aspirin and/or clopidogrel. Participation in the study is entirely voluntary. The alternative is not to participate in the trial.

8.8 ADVERSE EVENTS

8.8.1 Adverse Event (AE) Definitions

An AE is defined as any untoward medical occurrence in a patient or clinical investigation subject administered a pharmaceutical product which does not necessarily have to have a causal relationship with this treatment. An adverse event can be any unfavorable and unintended sign (e.g., including an abnormal laboratory finding), symptom, or disease temporally associated with the use of a drug, without any judgment about causality (i.e., whether or not it is considered to be drug-related). This includes any newly occurring event or previous condition that has increased in severity or frequency since the administration of the study treatment/intervention.

A suspected adverse reaction means any adverse event for which there is a reasonable possibility that the drug caused the adverse event. A suspected adverse reaction implies a lesser degree of certainty about causality than adverse reaction, which means any adverse event caused by a drug.

An adverse reaction means any adverse event caused by a drug. Adverse reactions are a subset of all suspected adverse reactions for which there is reason to conclude that the drug caused the event. An adverse event or suspected adverse reaction is considered "unexpected" if it is not

specifically mentioned as occurring with the particular drug under investigation. Information about common side effects already known about the study drug/s drug can be found in the study drug/s package inserts. This information will be included in the subject's informed consent and should be discussed with the subject during the study as needed.

8.8.2 Serious Adverse Event (SAE) Definition

An SAE is defined as an event that:

- is fatal or life-threatening;
- results in persistent or significant disability/incapacity;
- constitutes a congenital anomaly/birth defect;
- requires inpatient hospitalization or prolongation of existing hospitalization, unless hospitalization is for:
 - routine treatment or monitoring of the studied indication, not associated with any deterioration in condition
 - elective or pre-planned treatment for a pre-existing condition that is unrelated to the indication under study and has not worsened since the start of study drug
 - treatment on an emergency outpatient basis for an event not fulfilling any of the definitions of a SAE given above and not resulting in hospital admission
 - social reasons and respite care in the absence of any deterioration in the subject's general condition
- is medically significant, i.e., defined as an event that jeopardizes the subject or may require medical or surgical intervention to prevent one of the outcomes listed above

8.8.3 AE Grading Scale

The descriptions and grading scales found in NCI Common Terminology Criteria for Adverse Events (CTCAE) version 4.03 will be used for AE reporting. All appropriate treating areas should have access to a copy of the CTCAE version 4.0. A copy of the CTCAE version 4.0 can be downloaded (<http://ctep.cancer.gov>). This version of CTCAE is MedDRA v12.0 (Medical Dictionary for Regulatory Activities Terminology) compatible at the AE term level where each CTCAE term is a MedDRA LLT (Lowest Level Term). Each AE term is associated with a 5-point severity scale. Bleeding will be documented using the Bleeding Academic Research Consortium (BARC) standard definition (Appendix A) (Mehran et al., 2011).

8.8.4 Procedures for Recording and Reporting of Adverse Events

8.8.4.1 All AEs will be reported to the principal investigator and medical monitor for evaluation. For both serious and non-serious AEs, the investigator has the primary responsibility for AE identification, documentation, grading, and assignment of attribution to the study treatment/intervention. The sponsor will consider the investigator's view when assessing the safety of the drug and determining whether to report expeditiously to the FDA and other regulatory agencies.

8.8.4.2 AEs occurring from the start of study medication administration through the last day of study participation must be recorded on the AE CRF with the following information:

- The intensity grade (grade 1, 2, 3, 4, 5; see CTCAE v4.03 grading)
- The relationship to the study drug(s)

- Attribution: An assessment of the relationship between the AE and the medical intervention (i.e., study drug administration). After naming and grading the event, the clinical investigator must assign an attribution to the AE using the following attribution categories:

RELATIONSHIP	ATTRIBUTION	DESCRIPTION
Unrelated to study treatment/intervention	Unrelated	The AE is clearly NOT related to the study treatment/intervention
	Unlikely	The AE Is doubtfully related to the study treatment/intervention
Related to study treatment/intervention	Possible	The AE may be related to the study treatment/intervention
	Probable	The AE is likely related to the study treatment/intervention
	Definite	The AE is clearly related to the study treatment/intervention

- The duration (start and end dates or if continuing at final exam)
- Occurrence (known risks for study drug/s, underlying illness or population)
 - Expected
 - Unexpected
- Other contributing causes
- Action taken with study drug
- Any other actions in response to event
- Outcome
 - Death related to AE
 - Recovered/resolved with sequelae
 - Not recovered/resolved
 - Recovered/resolved without sequelae
 - Recovering/resolving
 - Intervention for AE continues
 - Unknown
- Whether it constitutes a serious adverse event (SAE)

8.8.5 AE Collection

The occurrence of adverse events should be sought by non-directive questioning of the subject at each visit during the study. AEs may also be detected when these are volunteered by the subject during or between visits or through physical examination, laboratory test, or other assessments. Medical conditions/diseases present before starting the study drug are considered AEs only if they worsen after starting the study drug. Abnormal laboratory values or test results constitute AEs only if they induce clinical signs or symptoms, are considered clinically significant, or require therapy. Abnormal values that constitute a SAE or lead to discontinuation of administration of study drug must be reported and recorded as an AE. Adverse event collection will commence when the subject starts taking study medication.

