8.2 Criteria for protocol review

Safety related criteria will be in place for continued dosing of subjects. If any of the criteria, listed below, are met, all available data will be reviewed by the principal investigator to provide a recommendation regarding subsequent enrollment.

- A serious adverse event (SAE), deemed related to study treatment, occurs.
- Any subject on treatment experiences bleeding (major or spontaneous).
- Any subject on treatment experiences a Common Terminology Criteria for Adverse Events (CTCAE; v4.03) Grade 3 (or higher) event, deemed related to study treatment.
- Any other event that occurs in a subject on active treatment that is deemed to pose an unacceptable risk to other subjects in the study.

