8.3.3 Adverse Events Collection

Identification of adverse events is important in monitoring for patient safety. Adverse events will be collected during each study visit using a combination of modalities which include, spontaneous reporting of AEs by the patient in response to an open question from study personnel, observation, physical examination, or other diagnostic procedures performed during the study. All subjects will be instructed to report any new or worsening signs and symptoms or clinical events. Adverse events will be reported and assessed for clinical significance by the investigator. Unscheduled clinic visits, additional safety laboratory tests, and other diagnostic procedures may be necessary as recommended by the investigator to evaluate subject safety and to further investigate AEs reported by subjects in-between scheduled clinic visits.

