17 APPENDICES

17.1 Appendix A: Bleeding Academic Research Consortium (BARC) definition for Bleeding

Type 0
 
 No bleeding

Type 1
 
 Bleeding that is not actionable and does not cause the patient to seek unscheduled performance of studies, hospitalization, or treatment by a health-care professional; may include episodes leading to self-discontinuation of medical therapy by the patient without consulting a health-care professional.

Type 2
 
 Any overt, actionable sign of hemorrhage (e.g., more bleeding than would be expected for a clinical circumstance, including bleeding found by imaging alone) that does not fit the criteria for type 3, 4, or 5 but does meet at least one of the following criteria: 
 requiring nonsurgical, medical intervention by a health-care professional, leading to hospitalization or increased level of care, or prompting evaluation

Type 3
 
 Type 3a: 
 Overt bleeding plus hemoglobin drop of 3 to < 5 g/dL* (provided hemoglobin drop is related to bleed) Any transfusion with overt bleeding Type 3b: 
 Overt bleeding plus hemoglobin drop ≥ 5 g/dL* (provided hemoglobin drop is related to bleed), Cardiac tamponade, Bleeding requiring surgical intervention for control (excluding dental/nasal/skin/hemorrhoid), Bleeding requiring intravenous vasoactive agents Type 3c: 
 Intracranial hemorrhage (does not include microbleeds or hemorrhagic transformation, does include intraspinal), Subcategories confirmed by autopsy or imaging or lumbar puncture, Intraocular bleed compromising vision.

Type 4
 
 CABG-related bleeding, Perioperative intracranial bleeding within 48 h, Reoperation after closure of sternotomy for the purpose of controlling bleeding Transfusion of ≥ 5 U whole blood or packed red blood cells within a 48-h period, Chest tube output more than or equal to 2L within a 24-h period

Type 5 (Fatal bleeding)
 
 Type 5a: Probable fatal bleeding; no autopsy or imaging confirmation but clinically suspicious

- **Type 5b:** Definite fatal bleeding; overt bleeding or autopsy or imaging confirmation

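### No bleeding question is specified, and one rule leaves most minor adverse events uncollected, so BARC Type 1 bleeds may be under-recorded

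*Combined protocol and SAP*

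**What the plan says.** **How events are sought.** Section 8.8.5: "The occurrence of adverse events should be sought by non-directive questioning of the subject at each visit during the study". It goes on: "AEs may also be detected when these are volunteered by the subject during or between visits or through physical examination", and also by laboratory tests or other assessments. Section 8.3.3 describes several routes together: "spontaneous reporting of AEs by the patient in response to an open question from study personnel, observation, physical examination, or other diagnostic procedures performed". It adds: "All subjects will be instructed to report any new or worsening signs and symptoms or clinical events".

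**How bleeding is classified.** Section 8.8.3: "Bleeding will be documented using the Bleeding Academic Research Consortium (BARC) standard definition (Appendix A". Section 8.8.6.1 repeats this. In Appendix A (17.1), Type 0 is no bleeding, and Type 1 begins: "Bleeding that is not actionable and does not cause the patient to seek unscheduled performance of studies".

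**What bleeding triggers.** Section 8.2 lists among its review criteria: "Any subject on treatment experiences bleeding (major or spontaneous". Section 8.4 stops treatment and removes the subject for the same two kinds of bleeding. *Spontaneous* is not defined in either place and is not a BARC category.

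**What is recorded.** Section 8.8.4.2 requires AEs from the start of study medication to the last day of participation to be entered on the AE form, with grade and attribution. Section 8.8.7 says that a non-serious AE is not collected unless it leads to discontinuation of study medication.

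**The concern.** Bleeding comes first among the drug risks in section 8.6.1.3, with a 55% increase in GUSTO moderate or severe bleeding. The synopsis calls the trial a safety investigation as well as a pharmacodynamic one. Yet no section requires anyone to ask a subject about bruising, nosebleeds, gum bleeding or any other bleed. If a subject does not raise a minor bleed, the record cannot tell BARC Type 0 from an unmentioned Type 1.

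Two uses of the data are at stake. First, the safety reviews after every 10 subjects (8.1.2) and the criteria in 8.2 and 8.4 can act only on bleeds that reach the record. Section 8.8.6.1 says that vorapaxar's effect has no known reversal and that briefly withholding it does not help in an acute bleed, which makes early knowledge of bleeding more useful. Second, any description of bleeding by BARC type will be least reliable at its lowest level.

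**Working it through.** The plan states no bleeding rate, detection rate or power, so there is no figure to reproduce. The check is mainly of the text, followed by an illustration on assumed inputs.

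**Step 1. Routes by which a minor bleed could be found.**
- Open question: at each visit (8.8.5, 8.3.3).
- Volunteered report: at any time. It is supported by the instruction to report symptoms (8.3.3), counselling on side effects (8.3.5) and reminders to make contact (9.2.3, 9.2.4). It still depends on the subject raising the bleed.
- Physical examination: after dosing, Table 1 (9.1) shows Visit 4 only. Figure 1 (2.1) also lists physical assessment at 24 hours and at end of study, which Table 1 does not carry. Section 8.3.4 mentions patient assessment at clinic visits.
- Laboratory tests: Table 1 has safety blood work, including a blood count, after dosing at Visits 4 and 6. A small bruise or nosebleed would rarely show there.
- Diary: run-in only (3.1.1), for drug intake.
- Directed bleeding question, questionnaire or bleeding diary: none in any section.

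**Step 2. Which BARC levels are exposed.** Only Type 1 is defined by the patient not seeking care. Types 2 to 5 are actionable, treated, supported by haemoglobin or imaging, surgical or fatal, and so are likely to surface by other means. The exposure is at the boundary between Types 0 and 1.

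**Step 3. Which triggers are exposed.** Major bleeding would usually come to notice. *Spontaneous* has no definition or stated severity floor, so a minor unprovoked bleed may or may not qualify. If it does, 8.2 and 8.4 act on an event that nobody is told to ask about.

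**Step 4. The recording rule.** Suppose a subject mentions a Type 1 bleed. Under 8.8.4.2 it is recorded. Under 8.8.7 it is not collected unless it leads to discontinuation. Whether it does so under 8.4 can turn on whether it counts as *spontaneous*, which is undefined. Read literally, 8.8.7 removes most Type 1 bleeds however they were elicited.

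**Step 5. Illustration on assumed values.** Let p be the true share of subjects with a minor bleed and s the share picked up; n = 25 per group (2.2).
- Expected number seen = 25 × p × s. For p = 0.10, s = 0.5: 1.25, against 2.5 with full detection. For p = 0.40, s = 0.9: 9.0, against 10.0.
- Chance that none is seen in a group = (1 − p × s)^25. For p = 0.10: 0.95^25 = 0.28 at s = 0.5, against 0.90^25 = 0.07 at s = 1.
- Two groups with assumed true rates of 0.10 and 0.30 (ratio 3.0, difference 0.20):
  - s = 0.5 in both: 0.05 and 0.15; the ratio stays 3.0 and the difference halves to 0.10.
  - s = 0.7 and 0.5: 0.07 and 0.15; ratio 2.14.
  - s = 0.5 and 0.7: 0.05 and 0.21; ratio 4.2.

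Unequal detection can therefore move a comparison either way, and nothing in the documents says which case applies.

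**The case against.** Open questioning is a legitimate method, applied in the same way to every group, and it is not the only route: 8.8.5 and 8.3.3 name others in the same breath. Not seeking care for a bleed is also different from not mentioning it when asked at a scheduled visit. Enquiry before vorapaxar is not absent: exclusion criterion 5 (2.6) covers bleeding history and active abnormal bleeding, 8.3.2 has the screening examination explore symptoms and risk factors, and Groups 2 to 4 have AE collection at run-in (9.1, 9.2.2). All of this stands, and it limits the point to minor bleeds and to the lack of a structured question.

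A reader might infer that bleeding as a whole will be under-counted. The documents do not support that: Types 2 to 5 do not depend on an open question in the same way.

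A reader might also infer that long-term aspirin or dual-therapy users will volunteer less than antiplatelet-naive subjects, so that the groups are biased against each other. That is conjecture. The opposite direction is as possible, the method is identical in all groups, and sections 5.2 and 6 plan no bleeding comparison. The open-label, non-randomized design with different background drugs makes unequal reporting possible, but gives neither size nor direction. One group difference is documented: run-in AEs are collected in Groups 2 to 4 only. That concerns the collection window, not the way of asking.

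**Conclusion.** The point holds for minor bleeding. The plan specifies no directed bleeding enquiry, and its two recording rules conflict in a way that could discard most Type 1 bleeds. BARC Type 1 bleeds, and minor bleeds that might count as *spontaneous*, are at risk of under-recording; it is not established that they will be under-recorded. The recording conflict is the firmer part, because it rests on the text alone. The enquiry gap rests on the reasonable assumption that some subjects will not mention a minor bleed unless asked.

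The size cannot be derived. Over the assumed range (p from 0.10 to 0.40, s from 0.5 to 0.9), 1.25 to 9.0 subjects per group would be seen, against 2.5 to 10.0 with full detection. No primary or secondary endpoint in 5.2 changes. This is an inexpensive improvement in safety data that should be made.

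**What to change.** 1. Reconcile 8.8.7 with 8.8.4.2, 8.3.3 and 8.8.5 so that every bleeding event is recorded, whether or not it is serious or leads to discontinuation. Until this is done, better questioning cannot be relied on to reach the data.
2. Keep the open question first. Then ask the same short, fixed set of bleeding questions in all four groups at each visit with AE collection, including Visit 2 before the first vorapaxar dose. Group 1 has no earlier AE collection, and 8.8.5 starts AE collection with study medication, so in that group the answers before dosing belong in baseline history.
3. Assign a BARC type (0 to 5) each time and flag each event as volunteered or elicited, so that volunteered events can still be tabulated alone.
4. The protocol authors should state what *spontaneous* means in 8.2 and 8.4 and reconcile it with the BARC types. Which bleeds should prompt review or stop treatment is for them to settle; no clinical rule is proposed here.

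The cost is a few questions per visit and a small addition to the case report form, with no extra staff. There are two downsides. More Type 1 events will be recorded. And, depending on how *spontaneous* is read, some elicited bleeds could meet 8.4 and remove subjects whom 8.5 says will not be replaced. Each subject lost before Visit 4 takes 1/25 = 4% of that group's data for the 3-4 week primary endpoint, so item 4 should be settled before the questions are introduced.

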8.8.6 Adverse Event Treatment

All AEs should be treated appropriately and managed as according to standard of care, at the discretion of the investigator. The action taken to treat the AE should be recorded on the AE CRF. A detected AE should be followed until its resolution or until the subject completes the study. Assessment should be made at each visit (or more frequently, if necessary) of any changes in severity, relationship to the study drug, the interventions required to treat it, and the outcome.

8.8.6.1 Treatment for Bleeding Events

Bleeding will be documented using the Bleeding Academic Research Consortium (BARC) standard definition (Appendix A) (Mehran et al., 2011). Bleeding events should be treated according to standard clinical practice, depending upon the location and severity of the bleed. Withholding vorapaxar for a brief period will not be useful in managing an acute bleeding event because of its long half-life. There is no known treatment to reverse the antiplatelet effect of vorapaxar.

8.8.6.2 Treatment for Allergic Reactions

Subjects will be observed for signs and symptoms of an allergic reaction while taking study drug/s and managed with appropriate therapy. The investigator may use his discretion in determining the regimen to be used according to standard clinical practice and tailored to the specific clinical situation (i.e., symptoms and severity of the reaction and responsiveness). Any occurrence of allergy signs and symptoms is cause for discontinuation of study treatment/s.

